5.1.2.2 Occurrence of Alopecia and Mucositis

Alopecia will be identified by the preferred term of ‘alopecia’, and mucositis will be identified by the high level term ‘stomatitis and ulceration’, or the preferred terms ‘mucosal inflammation’,

‘mucosal ulceration’, or ‘oesophagitis’ used in MedDRA Version 20.1 coding for AE data, and these terms will be used to identify the occurrence of events during the treatment period. Separate analyses will be done for each term.

Any occurrence of an alopecia (or mucositis) event during the treatment period is defined as a binary variable (Yes or No); Yes if total number of alopecia (or mucositis) events ≥ 1 is observed, No for other scenarios. Total number of events per subject will also be summarized. Data handling conventions for missing start/stop dates of AEs are in [Section 5.2.1](#).

5.1.2.3 FACT-L and FACT-An

The FACT-L is a 36-item self-report instrument that measures multidimensional quality of life (QoL) by asking patients to rate a series of statements. FACT-L consists of the 27-item FACT—general (FACT-G) combined with the 9-item lung cancer-specific subscale (2 of the 9 items are not scored, that is, B5 = “I am bothered by hair loss” and L5 = “I regret my smoking”).

The FACT-G contains four generic cancer-specific subscales including the 7-item physical well-being (PWB), 7-item social/family well-being (SWB), 6-item emotional well-being (EWB), and 7-item functional well-being (FWB) subscales. The 7-item Lung Cancer Subscale (LCS) assesses the impact of symptoms commonly reported by lung cancer patients, including shortness of breath, loss of weight, and chest tightness. The 20-item anemia subscale consists of the 13-item fatigue component and 7 items for non-fatigue; hence, fatigue and other symptoms of anemia (e.g., dizziness, joint aches, etc) are measured using an anemia-specific symptom scale that assesses self-report of the cognitive, physical, and emotional manifestations of anemia. All the questions are rated on a five-point Likert-type scale ranging from 0 (not at all) to 4 (very much).

Table 7 List of Items Which Need Subtraction before Subscale or Total Score Calculation

Subscale	Item ID	Items description	Value to be used for score calculation
PWB	All 7 items		4 - observed value
EWB	GE1	I feel sad	4 - observed value
	GE3	I am losing hope in the fight against my illness	4 - observed value
	GE4	I feel nervous	4 - observed value
	GE5	I worry about dying	4 - observed value
	GE6	I worry that my condition will get worse	4 - observed value
LCS	B1	I have been short of breath	4 - observed value
	C2	I am losing weight	4 - observed value
	L2	I have been coughing	4 - observed value
	L3	I feel tightness in my chest	4 - observed value
Anemia	HI7	I feel fatigued	4 - observed value
	HI12	I feel weak all over	4 - observed value
	An1	I feel listless (“washed out”)	4 - observed value
	An2	I feel tired	4 - observed value
	An3	I have trouble starting things because I am tired	4 - observed value
	An4	I have trouble finishing things because I am tired	4 - observed value

Subscale	Item ID	Items description	Value to be used for score calculation
	An6	I have trouble walking	4 - observed value
	An8	I need to sleep during the day	4 - observed value
	An9	I feel lightheaded (dizzy)	4 - observed value
	An10	I get headaches	4 - observed value
	B1	I have been short of breath	4 - observed value
	An11	I have pain in my chest	4 - observed value
	An12	I am too tired to eat	4 - observed value
	An14	I need help doing my usual activities	4 - observed value
	An15	I am frustrated by being too tired to do the things I want to do	4 - observed value
	An16	I have to limit my social activity because I am tired	4 - observed value

Calculation of the FACT scores and methods to deal with missing data will be handled according to the standard scoring guidelines. Based on the FACT scoring guide, [Table 7](#) identifies those items that must be subtracting the response from “4”. After the subtraction in proper items, the subscale score or relevant total score can be calculated. When there are missing data, a subscale with at least 50% answered items enables valid subscale score calculation (e.g., a minimum of 4 answered items from 7 items, 4 answered items of 6 items).

The total score is then calculated as the sum of the un-weighted subscale scores. However, two rules are defined as follows for a valid total score when there are missing data

- ALL of the component subscales have valid scores;
- at least 80% answered items in overall (e.g. e.g., at least 22 of 27 FACT-G items completed);

The detailed algorithms to calculate the subscale or relevant total score are defined in [Table 8](#). For both subscale and total score, higher scores represent better functioning and better QoL.

Table 8 Algorithm for Subscale Score and Total Score

Scale (no. of items)	Algorithm of score calculation
FACT-G (27)	
PWB subscale (7)	It is calculated as $7 \times [\text{Sum of item scores}] \div [\text{N of items answered}]$. If there are ≥ 4 missing items scores, the subscale score is set to missing. The subscale score ranges from 0 to 28.
SWB subscale (7)	It is calculated as $7 \times [\text{Sum of item scores}] \div [\text{N of items answered}]$. If there are ≥ 4 missing items scores, the subscale score is set to missing. The subscale score ranges from 0 to 28.
EWB subscale (6)	It is calculated as $6 \times [\text{Sum of item scores}] \div [\text{N of items answered}]$. If there are ≥ 4 missing items scores, the subscale score is set to missing. The subscale score ranges from 0 to 24.
FWB subscale (7)	It is calculated as $7 \times [\text{Sum of item scores}] \div [\text{N of items answered}]$. If there are ≥ 4 missing items scores, the subscale score is set to missing. The subscale score ranges from 0 to 28.
Total FACT-G score (27)	Sum of subscale scores from PWB, SWB, EWB, and FWB, then it is calculated as $27 \times [\text{Sum of subscale scores}] \div [\text{N of items answered}]$, however, 
 – if any of the subscale score is missing, the total score is set to missing; or

Scale (no. of items)	Algorithm of score calculation
	– if there are ≥ 6 missing items scores, the total score is set to missing; total FACT-G score ranges from 0 to 108.
LCS subscale (7)	
Total LCS subscale (7)	It is calculated as $7 \times [\text{Sum of item scores}] \div [\text{N of items answered}]$. If there are ≥ 4 missing items scores, the subscale score is set to missing. The subscale score ranges from 0 to 28.
Total FACT-L (FACT-G + LCS subscale; 34)	Sum of subscale scores from PWB, FWB, EWB, FWB, and LCS, then it is calculated as $34 \times [\text{Sum of subscale scores}] \div [\text{N of items answered}]$, however, 
 – if any of the subscale score is missing, the total score is set to missing; or – if there are ≥ 7 missing items scores, the total score is set to missing; total FACT-L score ranges from 0 to 136.
Trial Outcome Index (TOI) (21)	Sum of subscale scores from PWB, SWB, and LCS, then it is calculated as $21 \times [\text{Sum of subscale scores}] \div [\text{N of items answered}]$, however, 
 – if any of the subscale score is missing, the total score is set to missing; or – if there are ≥ 5 missing items scores, the total score is set to missing; TOI ranges from 0 to 84.
Anemia subscale (20)	
Fatigue subscale (13)	It is calculated as $13 \times [\text{Sum of item scores}] \div [\text{N of items answered}]$. If there are ≥ 6 missing items scores, the subscale score is set to missing. The subscale score ranges from 0 to 52.
Non-fatigue subscale (7)	It is calculated as $7 \times [\text{Sum of item scores}] \div [\text{N of items answered}]$. If there are ≥ 4 missing items scores, the subscale score is set to missing. The subscale score ranges from 0 to 28.
Total anemia subscale (20)	It is calculated as $20 \times [\text{Sum of item scores}] \div [\text{N of items answered}]$. If there are ≥ 11 missing items scores, the subscale score is set to missing. The subscale score ranges from 0 to 80.
Total FACT-An (FACT-G + anemia subscale; 47)	Sum of subscale scores from PWB, FWB, EWB, FWB, and anemia, then it is calculated as $47 \times [\text{Sum of subscale scores}] \div [\text{N of items answered}]$, however, 
 – if any of the subscale score is missing, the total score is set to missing; or – if there are ≥ 10 missing items scores, the total score is set to missing; total FACT-L score ranges from 0 to 188.
Anemia TOI (34)	Sum of subscale scores from PWB, SWB, and anemia, then it is calculated as $34 \times [\text{Sum of subscale scores}] \div [\text{N of items answered}]$, however, 
 – if any of the subscale score is missing, the total score is set to missing; or – if there are ≥ 7 missing items scores, the total score is set to missing; anemia TOI ranges from 0 to 136.

The extreme (best and worst) on study values and minimum and maximum change for each FACT subscale and total score will be derived.

Clinically meaningful improvement in LCS is a binary variable (Yes or No) — Yes if the LCS subscale score is $\geq 7\%$ increase from baseline, or ≥ 2 change from baseline, No for other non-missing scenarios. Similarly, clinically meaningful deterioration is a binary variable (Yes or No) — Yes if the LCS subscale score is $\geq 7\%$ reduction from baseline, or ≤ -2 change from baseline, No for other non-missing scenarios.

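### Programmed as printed, SAP Table 8 mis-scores five FACT totals: all five prorate for missing items twice, and the FACT-L and FACT-An totals count FWB twice and leave out SWB

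*SAP*

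**What the plan says.** All of this is in SAP section 5.1.2.3. The text above Table 8 gives the rule for totals: "The total score is then calculated as the sum of the un-weighted subscale scores". It also says that scoring and missing data follow the standard guidelines, and then: "The detailed algorithms to calculate the subscale or relevant total score are defined in" Table 8.

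Table 8 defines each subscale score as the number of items times the sum of item scores, divided by the number of items answered. The five total and TOI rows sum those scores and multiply again by total items over items answered. For FACT-G the row begins "Sum of subscale scores from PWB, SWB, EWB, and FWB, then it is calculated as" and continues with 27 times that sum over items answered; its stated range is "total FACT-G score ranges from 0 to 108".

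On components, the text says: "The FACT-G contains four generic cancer-specific subscales including the 7-item physical well-being (PWB), 7-item social/family well-being (SWB"), followed by EWB and FWB. The FACT-L row is labelled "Total FACT-L (FACT-G + LCS subscale; 34"), but its formula reads "Sum of subscale scores from PWB, FWB, EWB, FWB, and LCS, then it is calculated as" 34 times the sum over items answered. The FACT-An row, labelled as FACT-G plus the anemia subscale, lists the same four names before anemia, and its range sentence calls the score FACT-L.

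**The concern.** A score prorated at subscale level is already on its full scale, so scaling the sum a second time corrects for the same missing items twice. Separately, a FACT-L or FACT-An total without SWB is not FACT-G plus a disease subscale, whatever its label says.

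Five of the eight FACT lines among the exploratory efficacy endpoints in protocol section 13.4.1 are exposed: the general total, the FACT-L total and TOI, and the FACT-An total and TOI. Their changes from baseline and their best, worst and extreme-change values (SAP 5.1.2.3) are exposed with them. The second error is hard to see in output, because SWB and FWB each have 7 items and a 0 to 28 range.

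**Working it through.** **Inputs (SAP 5.1.2.3, Tables 7 and 8).** Items score 0 to 4. Items per subscale: PWB 7, SWB 7, EWB 6, FWB 7, LCS 7, anemia 20. Most missing items allowed, one fewer than each row's cut-off: FACT-G 5, FACT-L 6, TOI 4, FACT-An 9, anemia TOI 6. I take items answered to mean answered scored items, out of 34 for FACT-L and 47 for FACT-An.

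**Stated ranges on complete forms.** Maximum = 4 × items listed: FACT-G 4 × 27 = 108; FACT-L 4 × 34 = 136; TOI 4 × 21 = 84; FACT-An 4 × 47 = 188; anemia TOI 4 × 34 = 136. All five match Table 8. FACT-L and FACT-An match even with FWB doubled, since 7+7+6+7+7 = 34 and 7+7+6+7+20 = 47 with either subscale. The range check therefore cannot expose that slip.

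**Second proration.** Extra factor = total items K / items answered N.

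| Row | One missing | Most allowed missing | Factor applies to |
|---|---|---|---|
| FACT-G | 27/26 = 1.038 | 27/22 = 1.227 | intended sum |
| TOI | 21/20 = 1.050 | 21/17 = 1.235 | sum as listed |
| Anemia TOI | 34/33 = 1.030 | 34/28 = 1.214 | sum as listed |
| FACT-L | 34/33 = 1.030 | 34/28 = 1.214 | sum with FWB twice |
| FACT-An | 47/46 = 1.022 | 47/38 = 1.237 | sum with FWB twice |

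A form at the top of the scale with one item missing prints 108 × 27/26 = 112.2 for FACT-G, 84 × 21/20 = 88.2 for TOI and 136 × 34/33 = 140.1 for anemia TOI, each above its own stated maximum.

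Worked form (assumed): every answered item scores 3 and one PWB item is skipped. PWB = 7 × 18/6 = 21, and the plain sum is 21 + 21 + 18 + 21 = 81. Table 8 gives 27 × 81/26 = 84.1. With five items missing and the same answers it gives 27 × 81/22 = 99.4. With no real change, the error in change from baseline is +3.1 or +18.4 points if the follow-up form is the incomplete one, and the same size downward if it is the baseline form.

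**How often.** The documents give no item-missing rate, so I assume one. Items are missing independently of each other and of the score, with the Table 8 cut-offs applied to FACT-G (at most 3 missing per subscale, 5 in total).

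| Assumed item-missing rate | Scorable FACT-G forms affected | Rise in mean FACT-G |
|---|---|---|
| 0.1% | 2.7% | 0.10% |
| 0.5% | 12.7% | 0.52% |
| 1% | 23.8% | 1.05% |
| 2% | 42.0% | 2.12% |

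Exactly five missing items, which the 1.227 factor needs, occur in about 1 scorable form in 6,200 at 2% and 1 in 159,000 at 1%.

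**FWB for SWB.** On a complete form the error in FACT-L and FACT-An is FWB minus SWB, so between −28 and +28. Illustration (assumed values): PWB 20, SWB 24, EWB 18, FWB 14, LCS 18, anemia 50. FACT-L should be 20+24+18+14+18 = 94; as listed it is 20+14+18+14+18 = 84. FACT-An should be 126; as listed it is 116.

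**Both errors together.** Take one PWB item skipped and PWB 28, SWB 28, EWB 24, FWB 14, LCS 28. The correct FACT-L is 122. Table 8 gives (28+14+24+14+28) × 34/33 = 108 × 34/33 = 111.3, which is too low. So for FACT-L and FACT-An the net error can go either way.

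**Cut-offs (minor).** The text sets a 50% rule for subscales and illustrates it with 4 of 6 items (67%). The EWB row accepts 3 of 6 (50%), which meets the rule but not the example. The fatigue row needs 8 of 13 (62%), although 7 of 13 (54%) meets the rule.

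**The case against.** The best defence is that the plan names an outside authority. SAP 5.1.2.3 refers to the standard scoring guidelines and protocol section 13.4.2.5 to the FACIT version 4 instructions. A programmer who follows those, or who notices that the row labels and the FACT-G row give the right components, may never implement Table 8 as printed. That stands, and it is why the point is conditional on literal programming. It does not dispose of it: the same section sends the programmer to Table 8 for the algorithms, and validation under SAP 6.1.1 includes consistency with a plan that here contradicts itself.

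One could also read the total rows as using raw item sums, so that scaling happens once. Table 8 defines the subscale score as the prorated value, and the raw reading need not agree with the plain-sum rule. If PWB items score 1, all others 4, and one PWB item is skipped, the prorated sum is 7+28+24+28 = 87.0, while the raw reading gives 27 × (6+28+24+28)/26 = 89.3.

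It is also fair to say that the outputs are exploratory. FACT data are only described (SAP 6.2.7.2), between-arm comparisons are confined to the prospectively defined endpoints (SAP 6.2.7), and the FACT model was dropped (SAP section 7). That limits the weight, and I accept it.

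Three stronger readings are tempting and not supported. A reader might infer that every incomplete form is inflated; the 111.3 against 122 example shows otherwise for FACT-L and FACT-An. Skipping one of the unscored lung items ("2 of the 9 items are not scored") should inflate nothing either. And a reader might suspect the TOI rows of a similar component error, but nothing in the documents contradicts the components listed there.

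**Conclusion.** The point holds: Table 8 is wrong as written on two counts, and both follow from the SAP's own text.

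- **Second proration, five rows.** It has no effect on complete forms. On a scorable incomplete form with a non-zero score, FACT-G and the two TOIs are always inflated, by 3.0% to 5.0% for one missing item and 21.4% to 23.5% at the most allowed. Under the assumed missing rates group means barely move; single-form values, such as the best score and the maximum change, are the most exposed.
- **FWB for SWB, two rows.** Every FACT-L and FACT-An total in which the two subscales differ is wrong, with or without missing items. For incomplete forms the inflation factor describes the net error only once SWB is restored or where FWB equals SWB.

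Subscale scores, including LCS and its responder definition, are unaffected. No between-arm test or prospectively defined result changes. It is still worth correcting, because the error is certain on the page, five reported scores depend on it, and range checks will not catch the FWB slip.

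**What to change.** In SAP Table 8:

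1. Delete the multiplier (total items over items answered) from the FACT-G, FACT-L, TOI, FACT-An and anemia TOI rows, so that each total is the plain sum of its prorated subscales. Keep the 80% completion rule, which the total-score cut-offs already follow.
2. Replace the first FWB with SWB in the FACT-L and FACT-An rows.
3. Correct the FACT-An range sentence, which names FACT-L.
4. As a minor item, reconcile the 50% subscale rule with its 4-of-6 example and with the fatigue cut-off, against the scoring guide that the SAP cites.

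The cost is one table edit and a matching check of the scoring program; no new data are needed. Items 1 to 3 leave every subscale score unchanged. Item 4 may change which incomplete EWB scores count as valid, and through them some FACT-G, FACT-L and FACT-An totals, or which fatigue scores do. The fatigue cut-off does not feed FACT-An, because the anemia score is computed directly from its 20 items.

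### SAP Table 8 discards fatigue scores with 7 of 13 items answered, against the SAP's own half-answered rule; separately, the text's 4-of-6 example conflicts with the EWB row

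*SAP*

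**What the plan says.** SAP section 5.1.2.3 gives a general rule for missing items: "a subscale with at least 50% answered items enables valid subscale score calculation". It illustrates the rule with "a minimum of 4 answered items from 7 items, 4 answered items of 6 items". For total scores it requires valid component subscales and "at least 80% answered items in overall". The detailed algorithms are then set out row by row in Table 8.

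- **Fatigue (13 items):** "If there are ≥ 6 missing items scores, the subscale score is set to missing. The subscale score ranges from 0 to 52". The item count is confirmed earlier in the section: "The 20-item anemia subscale consists of the 13-item fatigue component and 7 items for non-fatigue".
- **EWB (6 items):** "If there are ≥ 4 missing items scores, the subscale score is set to missing. The subscale score ranges from 0 to 24".
- **Total anemia (20 items):** "If there are ≥ 11 missing items scores, the subscale score is set to missing. The subscale score ranges from 0 to 80".
- **Each 7-item subscale:** missing at 4 or more missing items.

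The section says that scoring and missing data follow the standard guidelines. Protocol section 13.4.2.5 points to the FACIT version 4 scoring instructions. Neither guide is reproduced in the documents.

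**The concern.** The rule and the table should select the same forms, and for fatigue they do not. A patient who answers more than half of the fatigue items still gets no fatigue score.

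For EWB the conflict lies between a worked example and the table. A programmer who follows the example sets a form with three EWB answers to missing; one who follows the table scores it. The choice carries further, because Table 8 sets FACT-G, FACT-L and FACT-An to missing whenever a component subscale is missing.

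At stake are avoidable loss of valid fatigue scores and four scores per affected form (EWB and three totals) whose existence depends on which line is followed. Patient-reported quality of life is an exploratory objective in every portion of the study (SAP Table 1), and section 5.1.2.3 derives extreme values and changes for each FACT subscale and total.

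**Working it through.** **Inputs.** Item counts and limits come from SAP section 5.1.2.3 and Table 8. With n items and a Table 8 limit of m or more missing, the fewest answered items that still give a score is n − m + 1.

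Two readings of the rule were tried:
- at least half: minimum answered = n/2 rounded up;
- more than half, the reading that 4 of 6 would imply: minimum answered = (n/2 rounded down) + 1.

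Under either reading the implied limit is n − minimum answered + 1 missing items.

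| Subscale | n | Table 8 limit | Fewest answered and scored | Limit, at least half | Limit, more than half |
|---|---|---|---|---|---|
| PWB, SWB, FWB, LCS, non-fatigue | 7 | ≥ 4 | 4 (57.1%) | ≥ 4 | ≥ 4 |
| EWB | 6 | ≥ 4 | 3 (50.0%) | ≥ 4 | ≥ 3 |
| Fatigue | 13 | ≥ 6 | 8 (61.5%) | ≥ 7 | ≥ 7 |
| Total anemia | 20 | ≥ 11 | 10 (50.0%) | ≥ 11 | ≥ 10 |

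**Fatigue.** Six missing leaves 13 − 6 = 7 answered, and 7/13 = 53.8%. Both readings accept 7 and give a limit of 7 or more missing. Table 8's limit of 6 fits neither.

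Table 8 is also at odds with itself here. Suppose 6 fatigue and 4 non-fatigue items are blank. Both component scores are then missing, yet total anemia is scored, because 6 + 4 = 10 is below its limit of 11. With the fatigue limit at 7 this cannot happen: 7 + 4 = 11, which is exactly the anemia limit. That suggests a slip rather than a deliberate choice.

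**EWB.** Three missing leaves 3/6 = 50.0%. This meets the at-least-half rule, and Table 8 scores it. The worked example asks for 4/6 = 66.7%. So the example disagrees with the rule it illustrates as well as with the EWB row.

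**Carry-through for EWB.** With three EWB items blank and all else complete, the answered fractions are:
- FACT-G: 24/27 = 89%;
- FACT-L: 31/34 = 91%;
- FACT-An: 44/47 = 94%.

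All clear 80%, so the overall completeness rule does not settle the matter. Neither TOI row includes EWB, so those two scores are unaffected.

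**Total-score limits at 80%.** Minimum answered = 0.8n rounded up:
- FACT-G (27): 22, limit 6;
- FACT-L (34): 28, limit 7;
- TOI (21): 17, limit 5;
- FACT-An (47): 38, limit 10;
- anemia TOI (34): 28, limit 7.

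All five agree with Table 8.

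**The case against.** The best defence has three parts.

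First, Table 8 is nearly all correct. Under the at-least-half rule, seven of its eight subscale limits reproduce, as do all five total-score limits. This stands. A reader might infer that the table generally departs from the rule; it does not. One number does.

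Second, the EWB row obeys the written rule, since 3 of 6 is exactly half, and the row conflicts only with a parenthetical example. This also stands. A reader might go on to infer a more-than-half rule from that example and conclude that the EWB and total anemia limits are both wrong. The documents do not support that. No sentence states such a rule, nothing contradicts scoring anemia from 10 of 20, and the example may itself be the mistake. Adopting the stricter rule would also discard more forms.

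Third, the effect is small. The fatigue limit touches only the fatigue subscale, because total anemia has its own limit and FACT-An and the anemia TOI use the anemia score. Protocol section 13.4.1 lists no separate fatigue subscale among the FACT endpoints. SAP section 6.2.7.2 limits these endpoints to descriptive summaries, and section 7 drops the modelling of FACT scores. It can also be argued that Table 8, as the detailed algorithm, naturally controls. All this limits the importance of the point. But the SAP states no order of precedence between text and table, and following the table leaves the fatigue limit wrong.

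**Conclusion.** The fatigue limit is wrong as written under any reading of the half-answered rule. It affects forms with exactly 6 of 13 fatigue items blank.

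The EWB matter is a genuine inconsistency, but which figure is at fault cannot be decided from these documents. It affects forms with exactly 3 of 6 EWB items blank, and where the other items are complete it decides four scores.

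The documents give no count of such forms; the assumption is that there are few. A reader might also suppose that sicker patients leave more items blank, so that the loss is selective. That is plausible, but the documents do not address it and the conclusion does not rest on it. This is a minor correction that leaves the trial's main comparisons untouched.

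**What to change.** Change the fatigue row of Table 8 from 6 or more to 7 or more missing items. This holds whichever rule is adopted.

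Before unblinding, check the even-length subscales against the scoring guide the SAP cites, and make the text and table agree:

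- **If the at-least-half rule stands:** keep EWB at 4 or more missing and total anemia at 11 or more, and correct the example to 3 of 6.
- **Only if the guide requires more than half:** reword the rule, and set EWB at 3 or more missing and total anemia at 10 or more.

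Leave the 7-item rows and the 80% limits alone. The cost is a few numbers or words in one SAP section and the matching lines of the scoring program.

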#### 13.4.2.5. Analysis of Exploratory Efficacy Endpoints

Grade 2 or higher nephrotoxicity, alopecia, and mucositis will be summarized with the number and percentage of patients experiencing the event any time during the Treatment Phase. For tabulations performed based on data collected in Part 2, the difference between treatment groups will be calculated and reported as described for the incidence of hematologic toxicity.

The FACT scores will be calculated per the FACIT version 4 scoring instructions and summarized by visit. The change from baseline in each score will be calculated and presented at each postbaseline visit. Additionally the change from predose to Day 10 and change from predose to end of cycle values will be calculated and presented at each cycle. Analysis of covariance models may be performed for summaries on Part 2, similarly to those described in Section 13.4.2.1. The extreme (best and worst) onstudy values and minimum and maximum change will also be analyzed. The number and percent of patients that have clinically relevant improvements or deteriorations will be summarized.

A single composite endpoint taking into account multiple types of hematologic parameters and other clinically relevant measures is of interest to capture the efficacy of G1T28 + E/P therapy. A composite endpoint will be defined *a priori* in a SAP. Factors such as infection rate, toxicity rates, chemotherapy dose reductions and/or interruptions, incidence of transfusions, incidence of growth factor use, AUC, etc. may be included. The association between composite endpoints and best overall response, overall survival, and PFS may be explored.

Similarly, identifying a composite hematologic score that represents ANC, lymphocytes, platelets, and hemoglobin in a meaningful way will be defined *a priori* in the SAP.

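### In the SAP's rule for clinically meaningful LCS change, the 7%-of-baseline alternative makes the 2-point threshold redundant at every baseline above 0 and lets a one-item, 1-point shift count at baselines 1 to 14

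*SAP*

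**What the plan says.** SAP 5.1.2.3 (FACT-L and FACT-An) defines two yes/no variables for the LCS, beginning "Clinically meaningful improvement in LCS is a binary variable (Yes or No").

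- **Improvement** is yes for a rise of at least 7%, the text continuing "increase from baseline, or ≥ 2 change from baseline, No for other non-missing scenarios".
- **Deterioration** is yes for a fall of at least 7%, continuing "reduction from baseline, or ≤ -2 change from baseline, No for other non-missing scenarios".

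In both, the percentage is taken from baseline and the two conditions are joined by *or*. The same section gives the scale: seven scored items, each rated 0 to 4, with higher scores meaning better functioning. For the LCS, Table 8 states: "The subscale score ranges from 0 to 28". Incomplete forms are prorated by 7 divided by the number of items answered, since "a subscale with at least 50% answered items enables valid subscale score calculation".

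The use of these variables comes from Protocol 13.4.2.5: "The number and percent of patients that have clinically relevant improvements or deteriorations will be summarized". The LCS rule is the only definition of this kind that the SAP gives for any FACT score. SAP 6.2.7.2 limits the exploratory endpoints, including this one, to descriptive summaries.

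**The concern.** Two thresholds joined by *or* are useful only if each catches patients that the other misses. Here the scale is so short that 7% of a patient's baseline is always less than 2 points. The 2-point figure, which reads like the anchor for a meaningful change, does almost no work, and the rule reduces to 7% of baseline.

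This has two consequences. The smallest change that counts depends on where the patient starts, and it is lower for patients with more symptoms. For those patients it is also the smallest change that a complete form can record. The reported percentages would then include single-category movements on one item under a label of clinical meaning, and a reader of the tables could not tell these from changes of 2 points or more.

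**Working it through.** **Inputs (all SAP 5.1.2.3):** 7 scored items; each item 0 to 4; thresholds of 7% from baseline or 2 points; proration factor 7/n for n items answered, with at least 4 of 7 required.

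**Step 1. Reproduce the stated range.** 7 × 0 = 0 and 7 × 4 = 28, which matches Table 8.

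**Step 2. Is the 2-point arm ever needed?** 7% of the highest possible baseline is 0.07 × 28 = 1.96, below 2. For 7% to equal 2 points, the baseline would have to be 2 / 0.07 = 28.57, which is off the scale. So for any baseline above 0, a change of 2 points or more already meets the 7% arm. Enumerating every baseline/follow-up pair, with whole scores and with prorated scores for 4, 5, 6 or 7 items answered at either visit, gave one exception: baseline 0. There the percentage is undefined, and the 2-point arm alone can identify improvement.

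**Step 3. Smallest qualifying change on complete forms.** A 1-point change meets 7% when baseline ≤ 1 / 0.07 = 14.29. Check: 1/14 = 7.14% qualifies; 1/15 = 6.67% does not.

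| Baseline LCS | Smallest change that counts |
|---|---|
| 0 | 2 points (improvement only) |
| 1 to 14 | 1 point, either direction |
| 15 to 28 | 2 points, where the scale leaves room |

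So 14 to 13 is a clinically meaningful deterioration and 15 to 14 is not.

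**Step 4. Incomplete forms.** With n items answered at both visits, one category on one item is worth 7/n points. It is at least 7% of baseline while the raw item sum at baseline is 14 or less, that is, up to a prorated baseline of 7 × 14 / n.

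| Items answered | Value of one category | Counts up to baseline |
|---|---|---|
| 7 | 1.00 | 14.0 |
| 6 | 1.17 | 16.3 |
| 5 | 1.40 | 19.6 |
| 4 | 1.75 | 24.5 |

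**Step 5. Illustration, improvement only, baselines 1 to 14.** Assumptions, none of them from the documents: no true change; visit-to-visit change normal with mean 0 and SD s, rounded to whole points. Then P(change ≥ 1) = P(Z ≥ 0.5/s), the SAP rule, and P(change ≥ 2) = P(Z ≥ 1.5/s), a 2-point rule.

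| s | SAP rule | 2-point rule | Excess |
|---|---|---|---|
| 1.5 | 0.369 | 0.159 | 0.210 |
| 2.0 | 0.401 | 0.227 | 0.174 |
| 2.5 | 0.421 | 0.274 | 0.147 |
| 3.0 | 0.434 | 0.309 | 0.125 |

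The excess from the SAP rule is about 12 to 21 percentage points at a single assessment.

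**The case against.** The strongest reply is that little depends on this variable. Patient-reported quality of life is an exploratory objective, SAP 6.2.7.2 summarises it descriptively, and SAP 6.2.7 keeps between-treatment efficacy comparisons for the endpoints of 5.1.1. The LCS is also reported in other ways: Protocol 13.4.2.5 provides change from baseline by visit, and SAP 5.1.2.3 adds best and worst values and the extremes of change. All of this stands, and it is why the point is minor.

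The size is also uncertain. Neither document gives an LCS standard deviation or a baseline distribution, so the share of patients starting at 14 or below is unknown. On complete forms at baseline 15 or more, the SAP rule and a 2-point rule classify every patient identically. A 2-point rule would itself mislabel 16–31% of unchanged patients under the Step 5 assumptions, so only the excess belongs to the SAP's wording.

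A reader might infer more than the documents support:

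- *That the rule dilutes the difference between arms.* Lowering a cut-point can shrink or enlarge a difference in proportions, depending on the distributions. The direction is unknown.
- *That the Step 5 figures apply equally to deterioration.* The normal model ignores the floor at 0. From baseline 1, for example, a 2-point fall is impossible.
- *That false classifications build up over the twice-per-cycle questionnaires.* SAP 5.1.2.3 does not say whether the variable is per visit or at any time on study.
- *That the sponsor meant 7% of the scale range.* The two figures do agree on that reading (2/28 = 7.1%), but the text says from baseline.

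None of this rescues the wording. Neither document adds a whichever-is-larger clause or a minimum point change, and a programmer would code the rule as written.

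**Conclusion.** The defect holds as a matter of arithmetic on the SAP's own scale and wording. For every baseline above 0 the 2-point arm is redundant. On complete forms, 1 point suffices at baselines 1 to 14 and 2 points are needed at 15 to 28. Because *or* can only add patients, the reported percentages cannot be lower than under a 2-point rule, and the additions on complete forms are all 1-point shifts in the more symptomatic half of the scale.

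This structural result needs no assumption. The excess of about 12 to 21 percentage points in false improvements does: it rests on an assumed SD of 1.5 to 3 points and applies to one assessment of an unchanged patient at baseline 1 to 14. What is affected is the meaning of two descriptive percentages. No test or trial conclusion depends on them. Severity: minor.

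**What to change.** Before unblinding, amend the two definitions in SAP 5.1.2.3 in one of two ways:

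- keep the SAP's own absolute threshold alone (improvement = LCS change of +2 or more; deterioration = LCS change of −2 or less) and delete the percentage alternative; or
- state that 7% means 7% of the 28-point range, which is 1.96 points. On complete forms, where changes are whole points, this gives the same classification as 2 points.

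The cost is two sentences and a small programming change. Fewer patients will be classed as changed. A patient at baseline 0 or 1 cannot be classed as deteriorated: at 0 no fall is possible under any rule, and at 1 the only possible fall, 1 to 0, would no longer count.
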